D.3.1. Sample. A total of 536 participants will be recruited and randomized to either the BMI+SC or SC condition during the first four and a half years of the study. The proposed sample size is feasible based preliminary data (i.e., approximately one eligible participant per recruiting day). We will screen approximately 545 participants per year (in 1:1 format). Based on preliminary data, 22% of these participants ($n=119$) will meet eligibility criteria for the study. We estimate attrition during follow-up at approximately 25% based upon Preliminary Study 2, leaving approximately 91 participants per year (or a total of 416 across 4.5 years) for analysis.

D.3.2. Rationale for standard care control group. Ultimately it is important to determine whether the BMI is efficacious relative to a specific active comparison condition. However, it is first necessary to determine whether the BMI+SC works at all compared to SC, taking into account affective psychopathy scores. Approximately 50% of all MCPS clients are mandated through the court system to complete substance abuse treatment, though the number who do so is lower. For the proposed study, the SC condition will include individuals who receive levels of non-study intervention that vary widely, from none to substantial. This real world condition provides the potential for useful generalization of results to other supervision programs, and is an appropriate comparison for assessing a brief intervention that may best serve as an adjunct to SC. The SC condition will consist of no research-related intervention beyond the baseline assessment session, but we will measure and analyze all non-study treatment participation carefully. Individuals in MCPS do not receive substance use services onsite, though some are referred to community providers for treatment. For anyone involved in non-study treatment, we will measure number of sessions and type of treatment in order to ensure that comparisons between BMI+SC and SC take into account all extra-study treatment.

D.4. Overview of Study Appointments

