D.4.1. Recruitment. After hearing an announcement in which the study is outlined, individuals who are within their first two weeks of the program, are 18 and older, can speak English, and are interested in participating will meet with study personnel individually. Those who provide informed consent will be enrolled. The informed consent procedure will include a detailed description of study procedures. For individuals with poor reading ability, as determined by having participants read the first paragraph of the consent form aloud, all written materials will be read by study personnel. See Appendix C for a table of measures and the administration timeline.

D.4.2. Session 1: Substance use screen. The screening sessions will be administered in 1:1 format. After filling out a demographic information form, participants will be administered three brief self-report measures to characterize substance use: a 12-item measure of the frequency of use of specific drugs, the Drug Abuse Screening Test (DAST)⁵³ and the Alcohol Use Disorders Identification Test (AUDIT).⁵⁶ Participants will be paid \$5. Individuals who indicate a frequency of substance use of once per week or greater during the past 6-months and have a DAST score > 3 are eligible for the RCT, with the exception of persons who exhibit severe psychotic symptoms or significant cognitive impairment during the initial or baseline assessments.

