enhance the efficacy of the intervention and perhaps broaden its therapeutic effects to more participants. This update involves dropping the use of a decisional balance exercise in order to decrease the amount of time spent talking about positive drug use experiences – a practice that may be detrimental and may elicit cravings.^{63,64} Our BMI manual (Appendix B) includes the following steps: establishing rapport, asking permission to discuss drugs and providing feedback regarding the drug use assessment, exploring personal consequences of drug use, eliciting the gap between real and desired quality of life, and discussing readiness to change. The therapist then negotiates a written action plan, during which the participant is supported with empathy, verbal reinforcement, information about drug abuse and treatment providers, and a referral for treatment.¹⁵ Continuing care is important for substance users⁶⁵ and data show that having more than one BMI session significantly enhances outcomes,⁶⁶ thus we will include brief (20-30 minutes), flexible, follow-up intervention sessions (Weeks 2, 4, and 6). Each follow-up session will be preceded by an assessment of substance use since the last session by personnel who are blind to psychopathy and treatment status. The Week 6 follow-up will also include readministrations of the BART and Self-Regulation Questionnaire (mediators) to assess change in self-regulation since baseline. Individuals in the BMI+SC and SC conditions will receive the same number of assessments and the same compensation (\$50) for assessment time. Individuals in both the BMI+SC and SC conditions will be assessed for substance use and treatment contacts at Weeks 2,4 and 6 and again at 6 months.

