D.5.1. Objective measures. Due to the potential for underreporting of substance use, we will obtain breathalyzer and urinalysis drug screen results at each follow-up using Varian Testcup Pro 5, which provides results for THC, methamphetamines, cocaine, benzodiazepines, and morphine. Results will be used to provide an objective measure of substance use to be incorporated in a secondary analysis. For the assessment of recidivism, The New York State Division of Criminal Justice Services (DCJS) maintains a database of criminal charges and convictions across the state. We will contract with DCJS to provide data at 12 months following the intervention or baseline assessment. Additionally, MCPS maintains a database of county-wide charges and convictions. Because each database does not always capture all official charges and convictions, they will be combined for maximum sensitivity (as in Preliminary Study 1). Criminal charges will be used as the primary measure of recidivism. Finally, recent involvement in non-study interventions will be assessed at baseline as a potential confound, and during follow up for descriptive purposes. Based on the results of the primary analyses, this data may also be used in exploratory analyses to determine whether BMI+SC increased substance abuse services utilization. The Coordinated Care Services, Inc. (CCSI) database will provide a novel way to gain objective information about participant treatment contacts—including substance abuse treatment—during the follow-up period. This health surveillance database is maintained by the Monroe County Office of Mental Health and was utilized in Preliminary Study 1. This database is used to track county-wide service contacts, enabling us to obtain services use data even for individuals who are lost to follow up. Moreover, we are able to cross-reference the objective database with our self-report

measure of non-study treatment for increased sensitivity and to check the validity of self-report treatment data.

D.5.2. Assessing Mediators. We will conduct a thorough, multi-method assessment of commitment to

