**Brief Intervention for Justice-Involved Substance Users:
Harnessing Mechanisms of Change**

NCT03308877

04/01/2017

D.7. Data Analysis. A baseline check of randomness will be conducted for each variable collected. Categorical variables will be analyzed using chi-square tests; continuous variables with ANOVAs. To assess Hypothesis 1 continuous outcomes, Analysis of Covariance will be used. The effects of BMI+SC on commitment to change, self-regulation, and substance use will be assessed immediately following intervention. Longer term substance use effects will be examined at 6-month follow-up. For substance use toxicology results, logistic regression will be used. In all instances, alpha = .05; covariates will include gender, race, age, and the outcome baseline score of interest as well as any other variables found to differ at baseline. Additionally, effect sizes will be examined using marginal means.⁷¹ Structural equation modeling (SEM) will be used to test the hypothesis that the effect of BMI+SC on substance use will be mediated by increases in commitment to change and self-regulation (Figure 2).⁷² *Substance use status* at six month follow-up is the key outcome of interest. We hypothesize that effects on six month substance use are mediated, in part, by BMI+SC effects on commitment to change and self-regulation. Substance use status will be measured using two indicators, percent days abstinent and the urine screen result. *Commitment to Change* will be measured using two indicators at each time point, the Readiness Ruler and the CLEAR change talk score at both baseline and immediate post. Two indicators will also be used to assess *Self-Regulation* at baseline and immediate post: Self-Regulation Questionnaire scores and Balloon Analog Risk Task scores. Additionally, demographic variables will be statistically controlled for in the model (gender, age, race, ethnicity). The MPLUS statistical package⁷³ will be used for SEMs. To provide a metric for each latent construct and to identify the model, the first construct loading for each latent variable will be set at 1.0. A two-step approach examining the model will be undertaken.⁷⁴ First, using confirmatory factor analytic techniques, a test of the proposed measurement model will be conducted and any needed modifications to this model, including testing for measurement invariance over time, will be undertaken prior to examining model fit. The second step involves an examination of the structural portion of the model. The model suggests that BMI effects on substance use are not only direct, but also indirect, mediated by effects on commitment to change and self-regulation. Baseline substance use status, commitment to change, and self-regulation will be controlled for, aiding precision in detecting treatment effects. Fit of the model will be assessed using a chi-square statistic, as well as the more approximate fit indices of the root mean square error of approximation (RMSEA),⁷⁵ the comparative fit index (CFI),⁷⁶ and the standardized root mean square residual (SRMR). Using various cutoffs for fit assessment helps to minimize Type I and Type II errors.⁷⁷ Recommendations that adequate fitting models have $CFI > .95$, $RMSEA < .06$, and $SRMR < .08$ will be adopted here. BMI indirect effects on 6 month substance use will be tested using the bias-corrected confidence limits.⁷⁸ Significance will be assessed by whether or not the 95% confidence limits contain zero. The bias corrected approach has been shown to provide the most accurate confidence limits and greatest statistical power when compared with other existing approaches for detecting mediation.⁷⁸ Multi-group structural equation modeling will be used to test moderated mediation. Two groups (high vs. low/moderate on affective psychopathy) will be compared. We will isolate differences across models by first examining if measurement parameters are equal across groups. Model differences across groups will be tested using the chi-square difference test. Next, we will test for structural differences across groups, examining regression parameter estimates for equality, followed by an examination of latent variables' variances and means across the groups. Such moderated-mediation will allow for isolation of BMI effects on latent variable means, controlling for process differences across the groups. Four exploratory analyses will also be conducted. The first will examine longitudinal change in substance abuse using growth curve analyses. Substance use is measured at baseline, 4 times during the intervention period, and at 6-month follow-up (6 time points). Time will be modeled so that the intercept reflects baseline status and subsequent time points will be modeled as weeks from baseline. Both linear and curvilinear (quadratic) change

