D.7.1 Power, Missing Data, and Type 1 Error Protection. For analyses involving continuous mean differences Optimal Design software was used to assess statistical power. With a sample size of 416, we are adequately powered ($> .80$) to detect a small standardized effect with baseline covariates explaining 40% of the outcome variance (n required = 265 to achieve .80 power). Should baseline covariates explain only 30% of the variance, we are powered at .78 to detect small effects. The inclusion of baseline covariates typically improves precision (at the cost of degrees of freedom)⁷⁹ For the logistic analyses predicting urine screen substance use results and 12-month recidivism, power analyses were conducted using the Stata statistical software program. We are interested in the power of treatment status to significantly detect a difference in positive urine screens and violent recidivism by 12 months. In a likely scenario of 50% positive urine screens, we are adequately powered (.80) to detect a 14% or more difference in rates. Power improves slightly as the baseline rates drift away from 50%. Typical 12-month violent recidivism rates are 20%. Here, we are adequately powered to detect a 12% point difference in rates, even if average absolute baseline covariate correlation with treatment is .3. For the structural equation model to be tested,⁸⁰ our approach allows for the testing of a null hypothesis of not good fit, reversing the role of the null hypothesis in conventional tests of model fit, so that a significant result provides strong support for good fit. With an expected sample size of 416, adequate power ($> .95$) to reject an hypothesis of close fit ($RMSEA > .08$) with 94 degrees of freedom (df) given a population $RMSEA$ of .05 was obtained (proposed model including age, gender, 2 race variable = 94 df). Additionally, adequate power (.99) to reject a hypothesis of not-close fit was obtained. Here, if model fit is extremely good ($RMSEA < .01$), and we test the hypothesis that fit is not close, we have greater than .95 power to reject the null hypothesis that $RMSEA > .05$. Even if sample size drops to 300, power for both the hypothesis of close fit and the hypothesis of not close fit remains above .90. As more degrees of freedom are introduced with the addition of multi-group modeling (psychopathy, gender, race), power improves on the above estimates. For analyses examining mean and rate differences, pairwise deletion of missing data will be used, thus retaining all available information. As a form of sensitivity analysis, however, multiple imputation of missing data will be conducted, which has consistently demonstrated less biased parameter estimates than most other approaches to the handling of missing data.⁸¹ To help control for Type 1 error, the Benjamini-Hochberg (BH) method⁸² will be used to adjust for the multiple comparisons proposed. The BH method adjusts for multiple comparisons by controlling the false discovery rate instead of family-wise error rate. It is less conservative than the more traditional Bonferroni methods, yet still provides adequate protection against Type 1 error.

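### The mediation SEM leaves measured baseline common causes out of its unrandomised mediator-to-use path, so if BMI moves a mediator, a false indirect effect can be declared

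*SAP*

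**What the plan says.** SAP D.7 names two sets of controls for the SEM. The first is demographic: "Additionally, demographic variables will be statistically controlled for in the model (gender, age, race, ethnicity". The second is the baseline values of the model's own constructs, and the only reason given is precision: "Baseline substance use status, commitment to change, and self-regulation will be controlled for, aiding precision in detecting treatment effects". The degrees-of-freedom note in D.7.1 points to no wider set: "proposed model including age, gender, 2 race variable = 94 df". Mediation is declared when the 95% bias-corrected limits for the indirect effect exclude zero.

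A broader rule appears earlier in D.7, beside the ANCOVA and logistic models: "covariates will include gender, race, age, and the outcome baseline score of interest as well as any other variables found to differ at baseline".

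The protocol collects other baseline variables that could bear on both mediators and use:

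- D.4.2 (screening): "participants will be administered three brief self-report measures to characterize substance use". These include the DAST and AUDIT.
- D.4.3: the PDSQ and PCL-R at Baseline A, and the Economic Form-90 at Baseline B.
- D.5.1, on non-study treatment: "recent involvement in non-study interventions will be assessed at baseline as a potential confound, and during follow up for descriptive purposes". D.3.2 adds the aim that "comparisons between BMI+SC and SC take into account all extra-study treatment".

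None of these is listed as an SEM covariate. Affective psychopathy enters only as the grouping variable of the multi-group model. The SAP states no assumption about confounding of the mediator-to-use path. Its only sensitivity analysis is multiple imputation for missing data.

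**The concern.** An indirect effect is the product of two paths. The path from BMI to the mediator is a comparison of randomised arms. The path from mediator to 6-month use is an observational regression within the trial, and a variable that drives both ends of it biases the coefficient even when the arms are perfectly balanced on that variable. Severity of dependence, psychopathology, psychopathy and recent treatment are plausible candidates, and all are measured before randomisation.

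What is at stake is the conclusion about mechanism, which is in the trial's title. The ANCOVA and logistic comparisons between arms are not affected by this point.

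**Working it through.** **1. The plan's own SEM figures.** D.7.1 gives the power of the model-fit tests. With noncentrality (N - 1) x df x RMSEA^2, df = 94 and alpha = .05:

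- N = 416: 415 x 94 x .08^2 = 249.7; x .05^2 = 97.5; x .01^2 = 3.9. Power is 0.9998 for RMSEA .08 against .05, and 0.9996 for .05 against .01.
- N = 300: 0.996 and 0.986.

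These agree with the stated > .95, .99 and above .90. They concern fit only and say nothing about bias in an indirect effect.

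**2. Why an omitted cause matters.** Let g be the standardised effect of the common cause on both mediator and outcome, v the share of its variance not explained by the baseline terms, and s^2 the mediator's variance given arm and baseline terms. With a true mediator-to-use effect of zero, the expected fitted coefficient is

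b = g^2 x v / s^2, and the false indirect effect is a x b,

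where a is the BMI effect on the mediator. If a = 0 the product is zero, whatever b is. As an example, take v = 1 and a coefficient of .5 on the baseline mediator, so s^2 = 1 - .25 = .75. Then g = .3 gives b = .09/.75 = .12 and, with a = 0.3, an indirect effect of .036 SD. The standard error of b is about 1/sqrt(416) = .049, so b is about 2.4 standard errors from zero. For g = .1, b = .01/.75 = .013, or about 0.3 standard errors.

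**3. Simulation.** From the documents: N = 416 analysed, 1:1 allocation (208 per arm), 95% limits excluding zero as the rule, and baseline mediator and baseline use controlled. Assumed: one observed mediator, a = 0.3 SD, and g and the overlap with baseline as shown. True mediation is zero throughout. Share of trials declaring mediation:

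| Setting | g = .1 | g = .2 | g = .3 |
|---|---|---|---|
| Cause omitted, unrelated to baseline terms | 5% | 20% | 60% |
| Cause omitted, correlation .5 with them | 5% | 10% | 32% |
| Cause omitted, correlation .7 with them | 4% | 8% | 13% |
| Cause adjusted | 4-7% | 4-7% | 4-7% |
| Cause omitted, BMI does not move the mediator | at most 3% | at most 3% | at most 3% |

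**4. How firm these are.** The overlap rows depend on the residual variances assumed. I repeated the check with 3,000 trials per setting and Monte Carlo limits. Mediator and outcome had unit variance before the arm effect and a coefficient of .5 on their own baseline value, and each baseline value was correlated with the cause only. This gave 5%/17%/64% with no overlap, 5%/12%/47% at .5 and 5%/8%/25% at .7. Adjusted rates were 4-6%, and rates with a = 0 were at most 3%. The pattern is the same; the individual percentages are not precise.

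**5. With the planned interval.** A bias-corrected bootstrap with a = 0.3 SD and a residual mediator-outcome correlation of .1 (close to .3 x .3 = .09) declared mediation in 56% of trials. With a = 0 and residual correlations of .1/.2/.3, it did so in 5%/8%/6%.

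**The case against.** **A reader might infer that any mediator-outcome correlation can pass as mediation.** It cannot. The plan tests the BMI indirect effect, so BMI must also move the mediator, and that path is randomised. Less severe participants reporting better self-regulation is not enough by itself.

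**A reader might also infer that use at Weeks 2 and 4 precedes the mediators, so the causal order is reversed.** The documents support that order for only some measures. Protocol D.4.4 says that participants "will be assessed for substance use and treatment contacts at Weeks 2,4 and 6", and places the BART and a Self-Regulation Questionnaire at Week 6. But D.5.2 gives the Readiness Ruler and the Questionnaire after each intervention session and codes change talk within sessions, so some mediator measurements come before Week 2 or Week 4 use. Early use is also post-randomisation and may carry part of the BMI effect, so conditioning on it is a trade-off.

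**The baseline terms absorb some confounding.** This stands. DAST and AUDIT plausibly overlap with baseline use, and the table shows that overlap lowers the false rate substantially. Weak common causes (.1) do no visible harm.

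**The rule on variables that differ at baseline may cover the SEM.** It is stated with the ANCOVA and logistic models and is absent from the SEM list. It also selects on imbalance between arms, whereas a balanced common cause still biases the mediator-to-use path.

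**Psychopathy is already handled.** In part: it is the matching factor and the grouping variable, so mainly the pooled model is exposed.

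**The covariate list may be incomplete.** The model's figure is not in the text available to me, and the degrees-of-freedom note omits ethnicity, which D.7 includes, so that note is not exhaustive. The point rests on the written list in D.7.

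**Conclusion.** The concern holds in a conditional form. As written, the SEM does not adjust the mediator-to-use path for measured baseline common causes. If BMI moves a mediator, which is what the trial hypothesises, and if such a cause has standardised effects of about .2 to .3 on both mediator and use, mediation would be declared falsely more often than the nominal 5%. The rate is about 20% to 60% if the cause is unrelated to the baseline terms. It is about 10% to 32% at correlation .5 and 8% to 13% at .7, with higher values at .3 under the other variance set-up. Adjustment brings the rate back to about 4-7%.

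The documents give neither the BMI effect on the mediators nor the strength of any common cause. Those are assumptions, and a single observed mediator stands in for the latent model. The figures show direction and scale; they do not forecast this trial's error rate. The documents do not support saying that correlation alone would be reported as mediation, or that early use generally precedes the mediators.

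**What to change.** In SAP D.7, list the following as predictors of both mediators and the outcome in the SEM, chosen in advance and not by arm imbalance: baseline DAST, AUDIT, PDSQ total, affective psychopathy score (pooled model) and baseline non-study treatment use from the Economic Form-90. State the assumption that no further common cause of mediator and outcome remains. Report the residual mediator-outcome correlation that would bring the indirect effect to zero, for example by refitting with that residual correlation fixed at a series of values.

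A model with Weeks 2 and 4 use placed before the Week 6 self-regulation measures may be added as a secondary sensitivity analysis. It should carry the caveat that early use may itself transmit part of the BMI effect, and it should not decide whether mediation is claimed. Treatment contacts during follow-up should not simply be added as covariates, because the intervention includes a referral.

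The cost is SAP wording and a few more parameters: five covariates on two mediators and one outcome is 5 x 3 = 15 paths if each is a single variable. The 94 df and its fit-power statement would need recomputing. No new data are needed.

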**Brief Intervention for Justice-Involved Substance Users:
Harnessing Mechanisms of Change**

NCT03308877

04/01/2017

Study Design

D.3. Overview. We propose a rigorous RCT using a matched-pairs design to test *a priori* hypotheses based on the findings of Preliminary Study 2, while investigating the mechanisms by which people change. In line with renewed national efforts to promote reproducible science, this study is, among other things, an attempt to replicate the primary findings of our published work in a larger sample. We incorporate appropriate blinding, and validated, multi-method measurement of constructs. We will compare the efficacy of BMI+SC versus SC across two groups: a) individuals with low/moderate affective psychopathy (affective score < 5) and, b) individuals with high affective psychopathy (affective score > 5). In Session One, individuals who are within their first three weeks at MCPS will be recruited and briefly screened for substance use. Individuals who report substance use once per week or more and meet the Drug Abuse Screening Test cutoff score of 3 or higher⁵¹ will continue in the study. Session Two (Baseline Assessment A) will involve a brief assessment of general psychopathology and detailed assessment of psychopathy and frequency of use of a range of substances. Baseline assessment B will include assessment of putative mediators (self-regulation and commitment to change), along with an assessment of treatment services use over the past 6 months. After Baseline Assessment B, participants will be randomized (coin toss) to either BMI+SC or SC in pairs that are matched according to affective psychopathy level. That is, two individuals with low/moderate affective psychopathy will be randomized (one each) to either BMI+SC or SC. The same will occur with individuals who are high in affective psychopathy. The next session will occur as close to baseline as possible, followed by sessions at 2, 4, and 6 weeks post-baseline. These meetings will involve assessments of frequency and type of substance use (both groups), and the delivery of our BMI (treatment group only). The outcome variables will be 1) frequency of substance use (proximal; percent days abstinent at 6 months) and 2) violent criminal recidivism (distal; charges at 12 months).

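### The bias-corrected 95% limits that decide mediation are not a 5% test at N = 416 when one path is null and the other is small to moderate: simulated error is about 6 to 7.5%, depending on the strength of the other path

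*SAP*

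**What the plan says.** SAP section D.7 fits a structural equation model in which commitment to change and self-regulation carry part of the intervention effect to substance use at six months. The test is stated as follows: "BMI indirect effects on 6 month substance use will be tested using the bias-corrected confidence limits". The decision rule comes next: "Significance will be assessed by whether or not the 95% confidence limits contain zero". The reason given, on one citation, is that "The bias corrected approach has been shown to provide the most accurate confidence limits and greatest statistical power". Earlier in the same section the general level is set: "In all instances, alpha = .05". Limits at 95% imply the same nominal 5%.

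The word bootstrap does not appear in either document, but it is the natural reading of bias-corrected limits for an indirect effect. The plan gives no size for either mediation path, no power for the indirect effect, no check of the rule's error rate at the planned size, and no second type of interval. SAP section D.7.1 adds a Benjamini-Hochberg adjustment without saying how it applies to a rule based on confidence limits. Its power statement for the model ("With an expected sample size of 416, adequate power") concerns overall fit, not the indirect effect.

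**The concern.** An indirect effect is a product of two paths: intervention to mediator (a) and mediator to substance use (b). It is zero if either path is zero. The null that matters here is mixed: the intervention raises readiness, say, but readiness does not change use.

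Under such a null the bootstrap distribution of the product is skewed. Its median tends to lie nearer zero than the estimate, so the bias correction moves both limits away from zero. The rule can then reject more often than 5%, and part of its extra power comes from that.

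Mechanisms of change are in the trial's title, and Protocol section D.3 presents the study as a contribution to reproducible science. A claim that the intervention works through a given mechanism should carry the error rate that the plan states.

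**Working it through.** **Plan's own figure.** The only error rate to compare against is the nominal 5%. The documents give no simulated rate to reproduce.

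**Inputs.** Analysed N is 416 (Protocol D.3.1: "or a total of 416 across 4.5 years"; same figure in SAP D.7.1). Allocation is 1:1 in matched pairs (Protocol D.3), so 416 / 2 = 208 per arm. The stated attrition gives 536 x 0.75 = 402 instead; this scales test statistics by sqrt(402/416) = 0.98 and does not matter here. Path sizes are not given, so a range is used. The small effect that SAP D.7.1 plans for in mean differences is read as 0.2 SD, which is an assumption.

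**Rule.** Let z0 be the inverse-normal of P(ab* < ab-hat) over the resamples. The bias-corrected limits are the Φ(2 z0 − 1.96) and Φ(2 z0 + 1.96) quantiles of ab*. Percentile limits are the .025 and .975 quantiles. To illustrate: if P(ab* < ab-hat) = .52, then z0 = 0.050, and the lower limit moves from the 2.5% quantile to the Φ(−1.86) = 3.1% quantile.

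**Simulation.** One observed mediator, normal errors, no direct effect, 10,000 trials per setting, 1,000 resamples, Monte Carlo error about 0.25 points. Share of trials in which the limits exclude zero although the true indirect effect is zero, N = 416:

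| Non-null path | Bias-corrected | Percentile |
|---|---|---|
| neither | 0.5% | 0.1% |
| b = .05 | 1.7% | 0.6% |
| b = .10 | 4.8% | 2.1% |
| b = .14 | 7.1% | 3.8% |
| b = .20 | 7.2% | 4.8% |
| b = .26 | 6.9% | 5.2% |
| b = .39 | 5.7% | 4.8% |
| b = .59 | 5.7% | 5.4% |
| a = 0.1 SD | 1.8% | 0.6% |
| a = 0.2 SD | 4.7% | 2.1% |
| a = 0.3 SD | 7.4% | 4.2% |
| a = 0.4 SD | 7.4% | 4.9% |
| a = 0.5 SD | 7.3% | 5.5% |
| a = 0.8 SD | 5.9% | 5.1% |

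**Large-sample cross-check.** Take the null path's estimate as N(0,1) and the other's as N(z,1). Bias-corrected error by z: 1.4% at 1, 4.3% at 2, 5.8% at 2.5, 6.8% at 3, 7.6% at 4, 7.5% at 5, 6.4% at 6, 5.7% at 8, 5.5% at 12. The pattern is the same.

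**The plan's small effect.** Without covariates, 0.2 SD gives z = 0.2 x sqrt(416)/2 = 2.04, where the error is below 5%. With covariates explaining 40% of variance, z = 2.04 / sqrt(0.6) = 2.63. Interpolating, 5.8 + (0.13/0.5) x 1.0 = 6.1%. A direct simulation of that setting (4,000 trials, R² of 40% applied to both mediator and outcome) gave 6.4%, against 3.5% for percentile limits. With 30% it gave 6.0% against 3.0%.

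**Power when both paths are real.**

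| Setting | Planned rule | Bias-corrected, tightened to 5% error | Percentile |
|---|---|---|---|
| a = .3, b = .14 | .78 | .71 | .68 |
| a = .2, b = .14 | .52 | .43 | .40 |

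A separate run put the first and last columns at .76 and .68, and at .51 and .41. The loss is therefore 8 to 12 points. From the table, .78 − .71 = .07 of the .10 loss, and .52 − .43 = .09 of the .12 loss, disappears once the bias-corrected rule is held to 5%.

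**The case against.** The strongest reply is that this is a trade-off. Bias-corrected limits are better balanced when mediation is real: simulated misses on the two sides were about 2.4% and 2.3%, against 1.7% and 3.9% for percentile limits. The excess is at most about 2.5 points at N = 416, and switching gives up power. The balance point stands, and it is why the bias-corrected limits should still be reported. The power argument mostly fails, because a bias-corrected rule held to 5% has nearly the same power as percentile limits.

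It can also be said that the simulation is simpler than the plan, which has two latent mediators with two indicators each, covariates, and an outcome that includes a urine screen. That stands: the direction is well supported, the exact size is not.

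Four stronger readings are tempting and not supported.
- A reader might infer that the error is inflated whenever one path is null. It depends on the other path, and below about z = 2 it is under 5%.
- A reader might take the inflation as 1.6 times nominal or more. A run of 2,000 trials did reach 8.3%, but its Monte Carlo error is about 0.6 points; the larger run peaks at 7.4%.
- A reader might infer that the same limits decide the psychopathy, gender and race comparisons. SAP D.7 tests psychopathy-group differences by chi-square difference and equality of parameters, and states no confidence-limit rule for any between-group comparison. The gender, race and recidivism models are exploratory.
- A reader might conclude that the accuracy sentence is false. The check covers rejection under a zero indirect effect; the cited source is not available, and the balance result partly favours the plan.

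The Benjamini-Hochberg step does not settle the matter, since it cannot repair a single test that is already liberal.

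**Conclusion.** The point holds in a conditional form. At N = 416 with one path null, the planned rule rejects about 6 to 7% of the time if the other path is 0.2 SD with covariates explaining 40% of variance. The figure is about 7 to 7.5%, or 1.4 to 1.5 times nominal (7/5 and 7.5/5), if the other path is moderate: an intervention effect of about 0.3 to 0.5 SD, or a mediator slope of about .14 to .26. Outside that range the excess is small or absent. Percentile limits did not exceed 5.5% in the main simulation.

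This rests on reading the limits as bootstrap limits, on a single observed mediator with normal errors, on path sizes that the plan does not state, and, for the covariate setting, on applying the 40% to the mediator as well. It is a modest but avoidable departure from the stated level, in the test that supports the trial's mechanism claim. It is worth changing before the analysis and does not threaten the design.

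**What to change.** In SAP section D.7:
- Name the method as a bootstrap. Make percentile bootstrap 95% limits the decision rule for the intervention's indirect effects on six-month substance use, and for any other indirect effect that is tested by confidence limits.
- Report bias-corrected limits from the same resamples alongside, as interval estimates.
- Qualify the sentence on accuracy and power so that it does not imply a 5% error rate.
- Leave the chi-square difference and parameter-equality tests between groups as they are.

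The change is a few sentences and one software option, with no new data or resampling. The price is the fall in nominal power shown above and somewhat less balanced limits when mediation is real.
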